#### 4 Volumetric Magnetic Resonance Imaging (vMRI) for the Research Study

Results of a study of vMRI versus cognitive testing demonstrate that vMRI could become the principal outcome measure for clinical trials in AD due to its precision. The vMRI scan should cover the entire brain (including cerebellum) and skull, superiorly and laterally. In the anterior/posterior plane the nose should also be included, otherwise image folding will result and the exam may not be usable for the study. To ensure scanner stability and scan quality throughout the study, each site is required to perform on-going quality control scans on an MRI phantom (such as Alzheimer's disease neuroimaging initiative phantom, American College of Radiology-ACR phantom, etc.) using the localizer and 3D T1-weighted scan prior to site scanning their first subject (prior to the screening), and then semi-annually throughout the remaining study period, as well as after any hardware upgrades to the scanner. If a site fails to perform these phantom scans prior to scanning study subjects, the study coordinator and the principal investigator at each site should be notified.

The most important image set is the T1-weighted 3D volumetric acquisition. Isotropic voxels are desired to avoid a directional bias, but not required. The target voxel size is approximately 1 mm^3, with a maximum of 1.5 mm in any one direction. The following is an example of a typical magnetization-prepared rapid gradient echo (MP-RAGE) sequence using a Siemens Trio 3-Tesla scanner for reference purpose: 128 slices, TR/TE = 2530/3.39 ms, slice thickness = 1.0 mm, flip angle = 7°, inversion time = 1100 ms, FOV = 256 × 256 mm, and in-plane matrix size = 256 × 256. Sites should acquire a 3D T1-weighted scan with scan parameters that are close to the MP-RAGE sequence mentioned above, compensating for differences in parameters based on their scanner manufacturer.

Proper placement in the head coil is crucial because scans are acquired straight, not in an oblique orientation. It is mandatory to use the same position at the time of baseline and all subsequent visits. Position on mid-sagittal slice from tri-planar scout and make sure to get full brain coverage without image wrap: the skull must be fully included superiorly and laterally and the entire cerebellum should be included inferiorly. Every subject for the study must receive a clinical check by an on-site radiologist at each MRI facility. A request for a repeat MRI may be required in the event that the scans are found to be unacceptable due to subject motion or an incomplete MRI acquisition. Repeat MRI scans should be performed as quickly as possible.

The vMRI data should be reviewed for quality at each site prior to sending the images to the Central Imaging Corelab, and if there are any artifacts, the scan should be repeated to get high quality images. Hippocampus and other brain regions (such as whole brain, ventricles) shall be assessed

using a semi-automatic, atlas based brain segmentation technique, and will be over-read by an independent reviewer (a qualified neuroradiologist), to capture volumetric measures. Volumetric data shall be corrected for differences in head size by dividing each measurement by the estimated total intracranial volume which is computed as the sum of the volumes of all four ventricles, the white matter, the gray matter, with the brain stem excluded.

The vMRI will be conducted at the first screening, at week 48 and week 78.

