The pathology of AD is characterized by a progressive loss of neurons and synapses with the presence of large numbers of extracellular amyloid plaques and intracellular neurofibrillary tangles. Although symptomatic therapies are available, there is still no proven treatment that can address a variety of neurobehavioral disturbances and reverse progression of AD. Increased amyloid beta (A $\beta$ ) production or reduced A $\beta$  catabolism has been implicated in the pathogenesis of AD. Therapeutic targets have focused on reducing A $\beta$  deposition in brain and evidence shows that antibodies targeting A $\beta$  can improve symptoms of AD. Results from successful immunotherapy with aggregated A $\beta_{1-42}$  in transgenic mice overexpressing A $\beta_{1-42}$  peptide led to the development of the first human active immunization trial with synthetic aggregated A $\beta_{1-42}$  peptide AN1792 in combination with QS-21 adjuvant. Analysis of AN1792-treated subjects showed that about 20% developed robust antibody response but available data on efficacy showed no significant effects on exploratory measures of cognition (Alzheimer's Disease Assessment Scale – Cognitive subscale [ADAS-Cog]) or disability (Disability Assessment for Dementia [DAD], Clinical Dementia Rating [CDR], Mini Mental State Examination [MMSE]). However, significant improvements were observed in a nine component neuropsychological test battery (NTB), indicating less worsening of performance in anti-A $\beta$  antibody responders. Improvements in memory were associated with increased antibody response and decreased tau in the cerebrospinal fluid in a small subset of patients. The AN1792-treated subjects were examined by magnetic resonance imaging (MRI) for cerebral volume changes; greater decrease of brain volume was noted without cognitive decline in antibody responders. Postmortem observations from three patients showed brain regions that were devoid of amyloid plaques. Unfortunately, the trial was halted after reports of acute meningoencephalitis in 18 of 300 patients treated with AN1792.

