## **APPENDIX 1: IMAGING PROTOCOL**

### **1 Introduction**

Since amyloid-modifying therapeutic agents have entered Alzheimer’s disease (AD) clinical trials over the past decade, the occurrence of imaging abnormalities has required careful consideration by pharmaceutical companies and regulatory authorities. Brain imaging in AD has undergone revolutionary changes with the wide availability of an unprecedented array of new techniques. 18F-AV-45 positron emission tomography (PET) exhibits high affinity specific binding to amyloid plaques. Since a negative 18F-AV-45 PET scan result reduces the likelihood that a patient’s cognitive impairment is due to AD, it can be an adjunct to other diagnostic evaluations. Various magnetic resonance imaging (MRI) methods are typically used in clinical trials of mild cognitive impairment (MCI)/AD for three purposes: 1) Eligibility and enrichment; 2) Safety: monitor side effects related to the study drug. 3) Efficacy: provide quantitative imaging biomarkers to assess drug effects on neurodegeneration longitudinally.

It is standard practice in AD trials to exclude patients with radiological evidence of space-occupying lesions, major vascular disease or infarct. Since the clinical diagnosis of AD during life is frequently inaccurate outside of research centers, 18F-AV-45 PET may have value as an adjunct to clinical diagnosis. For some amyloid-modifying therapies, microhemorrhages are a risk factor for drug side effects. The safety MRI assessments focus on the recently described amyloid-related imaging abnormalities (ARIA) seen in therapies directed at amyloid pathway modification, “vasogenic edema” and/or sulcal effusion (ARIA-E) and hemosiderin deposits (ARIA-H), including microhemorrhages and superficial siderosis. The volumetric MRI (vMRI) acquisition and derived metrics assess the neurodegenerative consequences of the disease and potential therapeutic alteration on both regional and whole brain structures. Resting-state functional MRI (rs-fMRI) is an imaging method that reflects synaptic activity through changes in blood flow and the deoxyhemoglobin to oxyhemoglobin ratio, and the structures that are particularly vulnerable for early amyloid deposition in AD appear to overlap with the heteromodal cortices of the default mode network.

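### The vMRI head-size divisor is labelled total intracranial volume but omits CSF outside the ventricles; if it is recomputed at each visit, it shrinks with atrophy and understates brain-volume loss.

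*Protocol*

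**What the plan says.** The rule is in Protocol Appendix 1, section 4, "Volumetric Magnetic Resonance Imaging (vMRI) for the Research Study".

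- What is measured: "Hippocampus and other brain regions (such as whole brain, ventricles) shall be assessed".
- When: "The vMRI will be conducted at the first screening, at week 48 and week 78".
- The correction: "Volumetric data shall be corrected for differences in head size by dividing each measurement by the estimated total intracranial volume".
- How the divisor is obtained: "computed as the sum of the volumes of all four ventricles, the white matter, the gray matter, with the brain stem excluded".

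The introduction to Appendix 1 gives the purpose: the volumetric metrics are to "assess the neurodegenerative consequences of the disease and potential therapeutic alteration on both regional and whole brain structures".

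The section does not say whether a subject has one divisor for all scans or a new one at each scan. vMRI is not among the endpoints in Protocol section 3.2 or SAP sections 2.3 to 2.5, and the SAP contains no vMRI analysis.

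**The concern.** A head-size correction needs a quantity that reflects the skull and does not move with the disease. The space inside the skull holds brain, ventricles, and the CSF in the sulci and cisterns. The plan's sum leaves out the last of these. When cortex shrinks and sulcal CSF takes its place, the lost volume leaves the divisor as well as the numerator.

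Two consequences follow:

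- **At any single scan**, including screening, a subject with more sulcal atrophy gets a smaller divisor than another subject with the same skull. The correction therefore mixes head size with disease.
- **Over time**, if the divisor is recalculated at Week 48 and Week 78, part of the true tissue loss divides out. A between-arm difference in atrophy would be compressed in the same way.

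Whole-brain change is of real interest here. Protocol section 1 reports that, with the earlier AN1792 vaccine, "greater decrease of brain volume was noted without cognitive decline in antibody responders".

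**Working it through.** The plan states no figure on this point, so there is none to reproduce. The check is algebra on the stated definition, followed by assumed values.

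**From the documents:** the divisor is D = T + V, where T is gray plus white matter without brain stem and V is the four ventricles. The measures are whole brain, hippocampus and ventricles, at three scans.

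**Assumed, because the documents give no volumes or rates:**

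- t = T/D = 0.95 at screening
- b = proportional tissue loss = 2%
- f = share of the lost tissue volume taken up by the ventricles, from 0 to 1 (the rest goes to CSF that D omits)
- h = proportional hippocampal loss = 3%, 5% or 8%
- the divisor is recomputed at each visit
- the whole-brain numerator is T

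**Formulas**

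- Divisor, relative to screening: R = 1 − (1 − f)·b·t
- Whole brain reads (1 − b)/R − 1. The share cancelled is 1 minus the reported loss divided by the true loss.
- Hippocampus reads (1 − h)/R − 1.
- Ventricles: true change is f·b·t/(1 − t). They read (1 + true change)/R − 1.

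**Worked case, f = 0.25**

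- R = 1 − 0.75 × 0.02 × 0.95 = 0.98575, so the divisor falls by 1.42%.
- Whole brain: 0.98/0.98575 − 1 = −0.58% instead of −2.00%. Cancelled: 1 − 0.583/2 = 71%.
- Hippocampus, h = 5%: 0.95/0.98575 − 1 = −3.63%. Cancelled: 27%.
- Ventricles: true +9.5%; 1.095/0.98575 − 1 = +11.1%.

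| f | Divisor | Whole brain reads (true −2.00%) | Cancelled | Hippocampus cancelled, h = 3% / 5% / 8% | Ventricles, true → reads |
|---|---|---|---|---|---|
| 0 | −1.90% | −0.10% | 95% | 63 / 37 / 22% | 0.0% → +1.9% |
| 0.25 | −1.42% | −0.58% | 71% | 47 / 27 / 17% | +9.5% → +11.1% |
| 0.50 | −0.95% | −1.06% | 47% | 31 / 18 / 11% | +19.0% → +20.1% |
| 0.75 | −0.48% | −1.53% | 23% | 15 / 9 / 5% | +28.5% → +29.1% |
| 1 | 0.00% | −2.00% | 0% | 0 / 0 / 0% | +38.0% → +38.0% |

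**Sensitivity.** Assumed volumes of 1000 mL tissue with 40 mL ventricles (t = 0.962) and 950 mL with 60 mL (t = 0.941) give 70–72% of whole-brain change cancelled at f = 0.25 and 46–48% at f = 0.50. The highest value, 96%, occurs at f = 0. These shares hardly change for b between 1% and 3%. The hippocampal share does depend on b relative to h: it equals the whole-brain share when the two shrink at the same rate, and it is smaller when the hippocampus shrinks faster.

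**Between arms.** With f = 0.25 in both arms, true whole-brain losses of 2.0% and 1.5% read −0.58% and −0.44%. A difference of 0.50 points becomes about 0.15.

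**One divisor per subject.** R = 1 at every visit, so nothing is cancelled from within-subject percent change for any structure.

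**A check that needs no volumes.** If whole brain is also measured without brain stem, T/D + V/D = 1. Corrected whole brain and corrected ventricles from the same scan are then one number. Section 4 does not define the whole-brain numerator, so this may hold only approximately.

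**The case against.** The strongest objection is that the cancellation over time rests on a step the text does not state. Dividing every measurement could mean every structure rather than every visit. The declared aim, differences in head size, is a between-subject aim that one divisor per subject would serve. This stands: recomputation at each visit is a plausible reading, but not an established one. The timing might also be settled in the separate research protocol, of which Appendix 2 gives only the title and number, or in the MRI Imaging Manual. Neither possibility alters the definition printed in section 4, which omits extra-ventricular CSF whenever it is computed.

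The sizes are also assumed. The result turns on f, about which the documents say nothing; at f = 1 the bias is zero.

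A reader might infer that the rule cancels most of the change in all three measures and so hides a treatment effect. The documents do not support that:

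- Only whole brain can lose about half or more of its change in the middle of the range.
- For the hippocampus, less than half is lost at those shares with 2% brain loss and 3–8% hippocampal loss.
- Ventricular change is slightly exaggerated, not cancelled.
- The report on the earlier vaccine does not say whether ventricles or sulci took up the lost volume. A ventricular signal would survive this rule.

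Finally, vMRI is an adjunct research measure, which limits the importance of the point but does not remove it.

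**Conclusion.** The concern holds in a limited form. The quantity is mislabelled: ventricles plus gray and white matter is not total intracranial volume, and it varies with atrophy as well as with head size. That much follows from the text alone.

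The bias over time is conditional on a divisor recomputed at each visit. On that reading, with tissue about 95% of the divisor, 2% brain loss and 25–50% of the lost volume going to the ventricles, about 47–71% of whole-brain change is cancelled (0–96% over all possible shares and the ventricle sizes tried). At the same shares, roughly 11–47% of a 3–8% hippocampal loss is cancelled, and ventricular enlargement is overstated by one to two percentage points. With one fixed divisor per subject, within-subject percent change is unaffected. The comparison of corrected volumes between subjects would still carry the labelling fault.

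The effect is confined to the adjunct vMRI measure; no primary or secondary conclusion of the trial depends on it.

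**What to change.** In Protocol Appendix 1, section 4:

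1. State that one divisor per subject, taken from the screening 3D T1 scan, is used for the screening, Week 48 and Week 78 volumes.
2. Also report within-subject percent change in raw volume, which needs no head-size correction.
3. Where the segmentation tool provides it, define the divisor as the full intracranial volume, including sulcal and cisternal CSF. Otherwise, rename it brain-plus-ventricle volume.
4. State whether the whole-brain numerator includes the brain stem.

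The imaging manual and the research protocol should carry the same wording, agreed before the volumes are analysed. Items 1, 2 and 4 need only text, because the scans and segmented volumes are already planned. Item 3 depends on the software: section 4 names only a semi-automatic atlas-based technique, so whether it yields a full inner-skull volume must be checked. No added scan or visit is needed.

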## 5 Resting state fMRI (rs-fMRI) for the Research Study

By measuring functional connectivity between spatially distinct brain regions, rs-fMRI can be used to evaluate brain function. Default mode network consists of the bilateral parietal cortex, the precuneus and posterior cingulate cortex, anterior cingulate cortex, medial prefrontal cortex, hippocampus, and thalamus. Previous rs-fMRI studies have shown a disruption in functional connectivity between structures that are part of the default mode network at an early stage of AD and MCI.

The higher resolution and shorter TR greatly enhances the ability to capture the spatial and temporal variations of brain activity and connectivity. The following is the recommended protocol: whole brain volume at  $2 \times 2 \times 2$  mm resolution within a TR of 720 ms and TE of 33-34.6 ms. It also requires the use of a 32 channel head coil (such as Nova Medical). Eyes open; 72 slices; 20.8 cm (A-P)  $\times$  18 cm (R-L) FOV; Matrix  $104 \times 90$ ; Flip angle  $52^\circ$ ; scan time:  $\sim 15$  min.

The rs-fMRI data will be pre-processed, including spatial smoothing with a 6 mm Gaussian kernel to produce default and attention networks robustly. The default mode network will be assessed by correlating each voxel in individual datasets with low frequency fluctuations within seed regions placed in the brain. This method correlates the average BOLD time course of voxels within these regions with each other and with the time courses of all other voxels in the brain.

The rs-fMRI should be conducted at the first screening, at week 48 and week 78.

## **APPENDIX 2: RESEARCH STUDY PROTOCOL**

A Research Study Adjunctive to a Randomized, Double-blind, Placebo-controlled, 3-arm Parallel-group, Multicenter, Phase IIa Study to Evaluate the Safety, Tolerability, Immunogenicity, and Efficacy of UBITH® AD Immunotherapeutic Vaccine (UB-311) in Patients with Mild Alzheimer's Disease (V203-AD). Protocol No.: V203-AD-Research.

SAE	Serious Adverse Event
SAP	Statistical Analysis Plan
SD	Standard Deviation
SUVR	Standard Uptake Value Ratio
TEAE	Treatment-emergent Adverse Event
TNF- α	Tumor necrosis factor-alpha
UNS	United Neuroscience Ltd.
V	Visit
W	Week
WBC	White Blood Cells
WHO	World Health Organization

AMENDMENT HISTORY

Date	Brief description of change
03Jun2016	Update per sponsor’s review comments.
02Jul2018	Update per sponsor’s review comments.
07Jul2018	Update per sponsor’s review comments.
05Sep2018	Update per sponsor’s review comments.
12Oct2018	Delete Center from mixed-effects model in section 5.9
29Oct2018	Add the words for “sensitivity analyses” in section 6

TABLE OF CONTENTS

LIST OF ABBREVIATIONS.....3

TABLE OF CONTENTS.....6

1 INTRODUCTION

This statistical analysis plan (SAP) is consistent with the statistical methods section of the final study protocol (Version 5.0, dated 28Nov 2017) and includes additional detail of efficacy, and safety summaries to be included in the clinical study report (CSR).

Specifically, this document will:

1. Briefly review the objectives, design and endpoints of the study
2. Define the analysis populations
3. Define the rules for determining the outcome of the endpoints
4. Provide an overview of the planned primary and secondary statistical analyses.

The planned analyses identified in this SAP will be included in regulatory submission and/or future manuscripts. Any post-hoc, or unplanned analyses will be clearly identified in the respective CSR. The reader of this SAP is encouraged to also read the clinical protocol for details on conduct of this study, and the operational aspects of clinical assessments and timing for completing a subject in this study.

2 STUDY OBJECTIVES AND ENDPOINTS

2.1 Primary Objectives

The primary objectives of this study are to assess the safety and tolerability of two regimens of UB-311, and to evaluate the immunogenicity of two regimens of UB-311 through measurement of anti-A β antibodies.

2.2 Secondary Objectives

The secondary objectives are to evaluate the effects of UB-311 on the changes of cognitive and functional performance over a period of 78 weeks, and to investigate whether UB-311 treatment results in changes in amyloid deposition in vivo by ¹⁸F-AV-45 PET imaging.

2.3 Primary Endpoint(s)

The primary endpoints of this study are:

- Safety and tolerability of UB-311 during the study period.
- The immunogenicity of UB-311 as measured by
 - Change from baseline in anti-A β antibody levels by the end of study.
 - Response rate.

2.4 Secondary Endpoint(s)

The secondary endpoints are:

- The change from baseline in cognitive, functional, and global assessments by the end of study, including:
 - Alzheimer's Disease Assessment Scale-Cognitive Subscale (ADAS-Cog)
 - Mini-Mental State Exam (MMSE)
 - Alzheimer's Disease Cooperative Study-Activities of Daily Living (ADCS-ADL)

- Clinical Dementia Rating-Sum of Boxes (CDR-SB)
- Neuropsychiatric Inventory (NPI)
- The change from baseline in amyloid deposition by the end of study, including:
 - Mean standard uptake value ratio (SUVR), a composite summary of selected brain regions by the end of study
 - Whole brain amyloid burden (positive or negative) determined by visual assessment

2.5 Exploratory Endpoints

- The change of standard uptake value ratio (SUVR) by region by the end of study.
- AUC of anti-Aβ antibody levels by the end of study.

3 STUDY DESIGN

This is a 78-week, multicenter, randomized, double-blind, placebo-controlled Phase IIa study. Eligible subjects, 60 years or older with mild Alzheimer’s disease (AD), will be further screened by ¹⁸F-AV-45 PET scan for the presence of amyloid deposition.

Enrolled subjects will be randomized into one of the 3 treatment arms in 1:1:1 ratio. Subjects assigned to Arm 1 will receive 7 doses of UB-311 at Weeks 0, 4, 12, 24, 36, 48, and 60.

Subjects assigned to Arm 2 will receive 5 doses of UB-311 at Weeks 0, 4, 12, 36, and 60, and placebo at Weeks 24 and 48. Subjects assigned to Arm 3 will receive placebo at Weeks 0, 4, 12, 24, 36, 48, and 60. Subjects will be followed until Week 78. Subjects enrolled in the Phase I trial with UB-311 will be excluded from the Phase IIa trial.

4 ANALYSIS VARIABLES

4.1 Demographic and Baseline Characteristics

The baseline value is defined as the last available value before the first injection of study drug. The following demographic and baseline disease characteristics will be summarized by treatment, by study center and overall for the randomized and treated population.

Demographic characteristics are defined as follows:

- Age (in years) to be derived as: (date of informed consent - date of birth)/365.25
- Gender (male/female)
- Body weight (kg)
- Body Mass Index (BMI, kg/m²): weight in kg/(height in meters)²
- Race

Disease characteristics including:

- Disease duration (years): (date of informed consent– date of diagnosis)/365.25
- APOE genotype
- Baseline scores of ADAS-Cog total score, MMSE total score, ADCS-ADL total score, CDR/CDR-SB total score, NPI total score

Inflammatory markers including:

- CRP
- ESR
- TNF- α
- IL-6
- IL-8

Physical examination, medical history and concomitant disease, previous and concomitant medication, and HIS score will be described at baseline.

The baseline safety data of clinical chemistry and hematology, inflammatory markers and number of microhemorrhages in the brain will also be summarized.

4.2 **Immunogenicity Variables**

The level of anti-A β antibodies is one of the primary endpoints and is assessed at baseline (V1) and every following visit (V2 to V13). The one-sided 95% confidence interval (CI, right side) from all visits (V1 to V13) for subjects in Arm 3 (placebo group) will be calculated as the threshold of response. Antibody responders will be defined as the subjects with serum antibody titer > response threshold at any visit after baseline.

Response rate, treatment difference and its 90% CI will be calculated.

The AUC of anti-A β antibodies will be served as exploratory endpoint. AUC will be calculated by the sum of individual trapezoid area under the curve of level of A β antibodies. In case of missing titer values, last observation carry forward will be used for AUC calculation.

4.3 **Efficacy Variables**

Efficacy variables are evaluated as secondary endpoints in this study.

The change from baseline in cognitive, functional, and global assessments through the end of the study

- Cognition: ADAS-Cog
 - The ADAS-cog 13 contains 13 items, with a total scoring range of 0 – 85 and higher scores indicating greater dysfunction.
- Cognition: MMSE
 - The MMSE is a 30-point questionnaire that is used extensively in clinical and research settings to measure cognitive impairment and is commonly used in medicine and allied health to screen for dementia. It is also used to estimate the severity and progression of cognitive impairment and to follow the course of cognitive changes in an individual over time; thus making it an effective way to document a participant’s response to treatment. The total score range is 0 – 30 and lower scores indicating greater impairment.
- Function: ADCS-ADL score is range of 0-78 and lower scores indicating greater impairment
- Global: CDR-SB

- The CDR-SB includes six domains (0-3 points/domain), with a total scoring range of 0 – 18 and higher scores indicating greater impairment. The CDR score is calculated at baseline for eligibility check.
- Behavior: NPI:
 - The NPI has 12 domains and for each domain, the relatives assess the frequency of the behaviour (4-point scale), the severity of the symptom (3-point scale) and the emotional stress for the caregiver (6-point scale). The total score of NPI is 0-144 and lower scores indicates greater impairment.

ADAS-Cog, ADCS-ADL, and NPI are rated at baseline (V1), Week 28 (V6), Week 52 (V10) and Week 78 (V13), while MMSE and CDR/CDR-SB are assessed at the first screening (S1), Week 24 (V5), Week 48 (V9) and Week 78 (V13). If a patient withdraws from the study prematurely during the study period or does not have any or some of the scores, the data will be treated as missing values, and no procedure for handling missing assessments will be applied.

